## 6. Have you been working with a statistician in designing this protocol? yes

**IF YES, what is their name?** [name], Senior Biostatistician, Department of Public Health Sciences.

**7. Will data from multiple sites be combined during analysis? No**

## Biomedical Research

**1. What will be done in this protocol?**

- Women age 40-69 years of age scheduled to undergo a screening mammogram at any one of our screening sites (Northridge, Orange, Zion Crossroads) or the UVa Breast Care Center will have their previous mammogram screened to see if there is evidence of heterogeneous or dense breast tissue (within 2 years). If so, the study nurse will contact the patient to see if they would like to participate in the CESM study. All patients having a CESM will have an appointment scheduled at the Breast Care Center, where CESM will be performed.
- In addition, study flyers approved by the IRB will be placed at UVa Imaging sites as well as primary care and gynecology offices.
- All women will have a urine pregnancy test at the Breast Care Center unless there has been no menstrual cycle for at least one year (postmenopausal) or history of hysterectomy.
- CESM is a mammogram performed after the injection of contrast via IV. Two images are taken almost simultaneously during the exam after the contrast is administered. The first image is essentially a standard mammogram. The 2nd image shows areas that take up the contrast (enhance) signifying increased blood flow. CESM studies are performed at the UVa Breast Care Center in the West Complex. Contrast administration is given following the same protocol of IV iodinated contrast administration as for CT scans elsewhere in the UVa Health System. Radiologists and technologists in the UVa Breast Care Center are trained in contrast administration and treatment of contrast reaction. Women having a CESM will have a 30 minute period post procedure to monitor for allergy to iodine contrast as per department SOP.
- Per department protocol, women age 60-69 will have serum creatine/GFR within 30 days or will have the test done prior to the CESM exam. If blood needs to be drawn prior to exam a BCC nurse or research nurse will draw 1 green top tube and send this to the Radiology Nursing area in main hospital. The blood will be processed for Creatinine and GFR on the I-STAT machine, results will be reported back to BCC. The standard mammogram portion of the CESM will be billed to the patients insurance as per standard of care. The administration of contrast and any cost related to the contrast enhanced portion of the CESM, will be paid for by the research study.
- All patients will undergo written consent for study participation after discussion of potential risks and benefits.

- Subjects who agree to participate in the CESM part of the study will complete a short survey regarding their interest and concerns about CESM PRIOR to the examination (Pre CESM Survey).
- The patient will then undergo CESM study which will serve as her annual breast imaging screening in place of annual screening mammogram.
- Since this is a screening exam, the study will not be interpreted immediately by the radiologist.
- Following the exam, the patient will be given a short survey (Post CESM Survey) that evaluates her experience during the CESM examination.

**2. List the procedures, in bullet form, that will be done for RESEARCH PURPOSES as stipulated in this protocol.**

- Contrast-enhanced Spectral Mammography (CESM) at Breast Care Center
- CESM pre and post surveys for women having CESM procedure only
- Urine pregnancy test for all pre-menopausal women having a CESM at the BCC.

**3. Will you be using data/specimens in this study that were collected previously, with the use of a research consent form, from another research study? No**

**4. Will any of the procedures listed in item # 2 have the potential to identify an incidental finding? This includes ALL procedures, assessments and evaluations that are being done for RESEARCH PURPOSES that may or may not be considered investigational.**

Yes. Although the anticipated enhancing lesions are expected to have a high incidence of carcinoma, benign lesions may enhance as well that would not be otherwise detected.

X The examination(s) utilize(s) the same techniques, equipment, etc., that would be used if the subject were to have the examination(s) performed for clinical care. **There exists the potential for the discovery of clinically significant incidental findings.**

- The PI takes full responsibility for the identification of incidental findings:
- The PI will inform the subjects verbally of all incidental findings that are of clinical significance or are of questionable significance.
- A follow-up letter describing the finding should be provided to the subject with instructions to either show the letter to their PC or if the subject has no PCP, the subject should be instructed to make an appointment at UVa or at the Free Clinic.

**5. Do any of the procedures listed above, under question # 2, utilize any imaging procedures for RESEARCH PURPOSES? Yes**

**IF YES, list procedures:** CESM

X This imaging research examination utilizes the same imaging techniques, equipment, scanning sequences that would be used if the subject were to have the imaging performed for clinical care. There exists the potential for the discovery of clinically significant incidental findings.

► If checked, answer the following:

**Will the images be read by a licensed radiologist and the reading placed in the subject's medical record? Yes**

**6. Will you be using viable embryos? No**

**7. Will you be using embryonic stem cells? No**

**8. Are any aspects of the study kept secret from the participants? No**

**9. Is any deception used in the study? No**

**10. If this protocol involves study treatment, explain how a subject will be transitioned from study treatment when they have completed their participation in the study. N/A**

**11. Will your study involve measures (C-SSRS/BID/SCID etc.) used to assess for depression and/or suicidality for research purposes? No**

## Data and Safety Monitoring Plan

### INSTRUCTIONS:

If you have any questions completing this section call [name] for assistance.

A Sponsor is defined as entity that will receive data prior to publication.

### 1. Definition:

#### 1.1 How will you define adverse events (AE) for this study?

An adverse event will be considered any undesirable sign, symptom or medical or psychological condition **even if the event is not considered to be related** to the investigational drug/device/intervention. Medical condition/diseases present before starting the investigational drug/intervention will be considered adverse events only if they worsen after starting study treatment/intervention. An adverse event is also any undesirable and unintended effect of research occurring in human subjects as a result of the collection of identifiable private information under the research. Adverse events also include any problems associated with the use of an investigational device that adversely affects the rights, safety or welfare of subject s.

#### 1.2 How will you define serious adverse events?

A serious adverse event will be considered any undesirable sign, symptom, or medical condition which is fatal, is life-threatening, requires or prolongs inpatient hospitalization, results in persistent or significant disability/incapacity, constitutes a congenital anomaly or birth defect, is medically significant and which the investigator regards as serious based on appropriate medical judgment. An important medical event is any AE that may not result in death, be life-threatening, or require hospitalization but may be considered an SAE when, based upon appropriate medical judgment, it may jeopardize the patient and may require medical or surgical intervention to prevent one of the outcomes listed in the definitions of SAEs.

**1.3 What is the definition of an unanticipated problem?**

**Do not change this answer**

An unanticipated problem is any event, experience that meets ALL 3 criteria below:

- Is unexpected in terms of nature, severity or frequency given the research procedures that are described in the protocol-related documents AND in the characteristics of the subject population being studied
- Related or possibly related to participation in research. This means that there is a reasonable possibility that the incident may have been caused by the procedures involved in the research study.
- The incident suggests that the research placed the subject or others at greater risk of harm than was previously known or recognized OR results in actual harm to the subject or others

**1.4 What are the definitions of a protocol violation and/or noncompliance?**

**Do not change this answer**

A **protocol violation** is defined as any change, deviation, or departure from the study design or procedures of research project that is NOT approved by the IRB-HSR prior to its initiation or implementation. Protocol violations may be major or minor violations.

**Noncompliance** can be a protocol violation OR deviation from standard operating procedures, Good Clinical Practices (GCPs), federal, state or local regulations. Noncompliance may be serious or continuing.

**Additional Information:** see the IRB-HSR website at

[http://www.virginia.edu/vpr/irb/HSR\\_docs/Forms/Protocol\\_Violations\\_%20Enrollment\\_Exceptions\\_Instructions.doc](http://www.virginia.edu/vpr/irb/HSR_docs/Forms/Protocol_Violations_%20Enrollment_Exceptions_Instructions.doc)

**1.5 If pregnancy occurs how will this information be managed?**

Other: Pregnancy status is determined prior to mammogram. Pregnancy excludes the subject from the study

**1.6 What is the definition of a Protocol Enrollment Exception?**

NA- No outside sponsor

**1.7 What is the definition of a data breach?**

**Do not change this answer**

A data breach is defined in the HITECH Act (43 USC 17932) as an unauthorized acquisition, access, or use of protected health information (PHI) that compromises the security or privacy of such information.

**Additional Information** may be found on the IRB-HSR Website: [Data Breach](#)

**2. Identified risks and plans to minimize risk**

**2.1 What risks are expected due to the intervention in this protocol?**

Expected Risks related to study participation.	Frequency
Radiation	 Occurs frequently  Occurs infrequently  Occurs rarely  Frequency unknown
Allergy to contrast :	
Mild reactions include: 
 
• nausea and vomiting
 
• headache
 
• itching
 
• flushing
 
• mild skin rash or hives
 
	 Occurs frequently  Occurs infrequently  Occurs rarely  Frequency unknown
Moderate reactions include: 
 
• severe skin rash or hives
 
• wheezing
 
• abnormal heart rhythms
 
• high or low blood pressure
 
• shortness of breath or difficulty breathing
 
	
Severe reactions include: 
 
• difficulty breathing
 
• cardiac arrest
 
• swelling of the throat or other parts of the body
 
• convulsions
 
• death
 
	
profound low blood pressure	
IV site infection	 Occurs frequently  Occurs infrequently  Occurs rarely  Frequency unknown

**2.2 List by bullet format a summary of safety tests/procedures/observations to be performed that will minimize risks to participants:** Adequate screening

**2.3 Under what criteria would an INDIVIDUAL SUBJECT'S study treatment or study participation be stopped or modified**

At subject, PI or sponsor's request

**2.4 Under what criteria would THE ENTIRE STUDY need to be stopped.**

**INSTRUCTIONS;**

- These are called stopping rules for early termination of the entire study.
- List criteria regardless of whether the study is sponsored or not.
- Be sure to include any criteria for which the UVa PI would halt the study at UVa.
- Check all that apply.

Per IRB, PI, DSMB

**2.5 What are the criteria for breaking the blind/mask?**

NA – Not blinded/masked

**2.6 How will subject withdrawals/dropouts be reported to the IRB prior to study completion?**

IRB-HSR continuation status form

**3. Adverse Event / Unanticipated Problem Recording and Reporting**

**3.1 Will all adverse events, as defined in section 1.1, be collected/recorded? NO**

► IF NO, what criteria will be used?

Only adverse events that are deemed related AND serious

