**3.2 How will adverse event data be collected/recorded?**

Spreadsheet: paper or electronic

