**3.4 What scale will the PI use when evaluating the relatedness of adverse events to the study participation?**

The PI will determine the relationship of adverse events to the study using the following scale:

Related: AE is clearly related to the intervention

Possibly related: AE may be related to the intervention

Unrelated: AE is clearly not related to intervention

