**3.6 When will the recording/reporting of adverse events/unanticipated problems end?**

End of study participation

**3.7 How will Adverse Events, Unanticipated Problems, Protocol Violations and Data Breaches be reported? Complete the table below to answer this question**

Type of Event	To whom will it be reported:	Time Frame for Reporting	How reported?
Any internal event resulting in death that is deemed DEFINITELY related to (caused by) study participation An internal event is one that occurs in a subject enrolled in a UVa protocol	IRB-HSR	Within 24 hours	IRB Online and phone call www.irb.virginia.edu/
Internal, Serious, RELATED, Unexpected adverse event	IRB-HSR	Within 7 calendar days from the time the study team received knowledge of the event.  Timeline includes submission of signed hardcopy of AE form.	IRB Online www.irb.virginia.edu/
Unanticipated Problems that are not adverse events or protocol violations This would include a Data Breach.	IRB-HSR	Within 7 calendar days from the time the study team received knowledge of the event.	Unanticipated Problem report form.  http://www.virginia.edu/vprgs/irb/HSR_docs/Forms/Reporting_Requirements-Unanticipated_Problems.doc
Protocol Violations/Noncompliance The IRB-HSR only requires that MAJOR violation be reported, unless otherwise required by your sponsor, if applicable.  OR Enrollment Exceptions See definition- only allowed if	IRB-HSR	Within 7 calendar days from the time the study team received knowledge of the event.	Protocol Violation, Noncompliance and Enrollment Exception Reporting Form  http://www.virginia.edu/vprgs/irb/hsr_forms.html  Go to 3rd bullet from the bottom.

there is a commercial sponsor or a DSMB that has granted the enrollment exception.
			

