**5. Data and Safety Oversight Responsibility**

**5.1. Who is responsible for overseeing safety data for this study?**

No additional oversight body other than PI at UVa Skip question 5.2

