**5.2. What is the composition of the reviewing body and how is it affiliated with the sponsor? n/a**

**5.3. What items will be included in the aggregate review conducted by the PI?**

- All adverse events
- Unanticipated Problems
- Protocol violations/Issues of noncompliance
- Audit results
- Application of dose finding escalation/de-escalation rules
  - These should be outlined under 2.4.
- Application of study designed stopping/decision rules
- Early withdrawals
- Whether the study accrual pattern warrants continuation/action
- Endpoint data

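### The adverse event record (section 3.1) is narrower than the aggregate review it feeds (5.3): non-serious contrast reactions, and on one reading serious possibly related events, need not be recorded

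*Protocol*

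**What the plan says.** All sections cited are in the protocol's Data and Safety Monitoring Plan unless stated otherwise.

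- Section 1.1 defines an adverse event broadly, with no requirement that it be serious or related.
- Section 3.1 asks whether all events so defined will be recorded, answers no, and gives the criterion: "Only adverse events that are deemed related AND serious". Section 3.2 names the medium: "Spreadsheet: paper or electronic".
- Section 3.4 sets three levels of relatedness. The top one is "Related: AE is clearly related to the intervention" and the middle one is "Possibly related: AE may be related to the intervention".
- Section 5.1 assigns safety oversight as follows: "No additional oversight body other than PI at UVa". Section 5.3 lists the contents of the investigator's aggregate review, the first being "All adverse events". Sections 5.4 and 5.6 make the review annual and send it to the IRB with the continuation form.
- Section 2.1 lists mild, moderate and severe contrast reactions among the expected risks. Under Biomedical Research, item 1, women are observed for 30 minutes after the procedure for contrast allergy.
- The table in section 3.7 sets the expedited routes to the IRB.

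**The concern.** The review in 5.3 draws on a record that 3.1 has already filtered. Under the definition in 1.1, an itching or hives reaction after contrast is an adverse event and so belongs in the review. It fails the seriousness condition of 3.1, so it need not be in the data reviewed.

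The second difficulty is the word related in 3.1. If it carries the meaning given in 3.4, a serious event judged possibly related falls outside the recording criterion.

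What is at stake is the content of the annual safety summary. The contrast injection is what the study adds to the screening visit, and the reactions the protocol expects from it are the ones its record may lack.

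**Working it through.** **Consistency of the text.** The protocol states no figure to reproduce, so the sections are compared directly.

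1. Scope of the review (5.3, with the definition in 1.1): every adverse event, of any seriousness and any relatedness.
2. Scope of the record (3.1): events that are both serious and related. This is a strict subset of step 1, so the review in 5.3 cannot be completed from the record.
3. A non-serious contrast reaction is in the first set and not in the second. Some moderate reactions could be judged serious under 1.2 and would then be recorded. The gap concerns those that stay non-serious.
4. Does 3.7 fill this gap? Its event rows cover "Any internal event resulting in death that is deemed DEFINITELY related to (caused by) study participation", "Internal, Serious, RELATED, Unexpected adverse event", and unanticipated problems that are not adverse events. A non-serious reaction fits none of them. The post-CESM survey asks about the patient's experience and is not described as adverse event recording.
5. Does 3.7 settle what related means in 3.1? It uses an intensified term for deaths and the plain term for serious unexpected events. That hints that the plain term is the wider one. Section 3.4 defines the same plain term as a clear relation and sets possibly related apart. The two point in different directions and nothing in the protocol decides between them.

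**Size.** The inputs are n = 210 (Human Participants) and a non-serious reaction rate p. The protocol gives only the lowest frequency category that it ticks, so p is an assumption, taken from 0.1% to 3%. Expected number = 210 × p. Chance of at least one = 1 − (1 − p)^210.

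| Assumed p | Expected number | Chance of at least one |
|---|---|---|
| 0.1% | 210 × 0.001 = 0.21 | 1 − 0.999^210 = 19% |
| 0.5% | 210 × 0.005 = 1.05 | 1 − 0.995^210 = 65% |
| 1% | 210 × 0.01 = 2.1 | 1 − 0.99^210 = 88% |
| 3% | 210 × 0.03 = 6.3 | 1 − 0.97^210 = 99.8% |

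**What recording would give.** Exact (Clopper-Pearson) two-sided 95% limits are:

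- 0 of 210: upper limit 1 − 0.025^(1/210) = 1.7%
- 2 of 210 (0.95%): 0.1% to 3.4%
- 6 of 210 (2.9%): 1.1% to 6.1%

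**The case against.** The list in 5.3 looks like form text left largely unedited. It also includes dose-escalation rules, which have no place in a single-visit imaging study. The entry on adverse events may simply mean those collected under 3.1, which is the study-specific answer, and the form allows limited recording. This is fair: rewording 5.3 alone would remove the mismatch. It would close neither gap in the record.

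A reader might infer that the annual review is the only safety oversight. The documents do not support that. Section 3.7 sends definitely related deaths to the IRB within 24 hours and serious, related, unexpected events within 7 calendar days. Section 2.4 also lets the IRB stop the study. What stands is that none of these routes captures a non-serious reaction.

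A reader might also infer that such reactions would go undocumented altogether. Observation follows a departmental procedure that is not among the documents, and a clinical note may well be made. The supported statement is only that they need not enter the research record.

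On relatedness, the wording of 3.7 gives some support to the wider meaning, so the omission of serious possibly related events is one reading and not a certainty. A one-line clarification is still justified.

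Finally, the assumed rates span a factor of 30 and cannot establish importance. That is correct. They show only how few rows are involved and what could be said if the rows existed.

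**Conclusion.** The point holds in a limited form and is worth correcting. Sections 3.1 and 5.3 do not agree. Non-serious contrast reactions that the protocol expects and observes for need not be recorded. Section 3.1 also leaves open whether a serious, possibly related event must be.

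The amount of missing information is small: about 0 to 6 reactions among 210 women, if the rate lies between 0.1% and 3%. No contrast-reaction rate is a planned endpoint, and no planned survey analysis, sample size or error rate is affected.

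It might be thought that 3.3 and 3.4 also contradict 3.1, since they provide classes that 3.1 would leave empty. They do not: a grading scale may contain levels that the recording rule never uses.

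**What to change.** Reconcile sections 3.1 and 5.3.

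1. In 3.1, record (i) serious events that are related or possibly related, and (ii) contrast reactions of any grade seen during the existing 30-minute observation, with the grade from 3.3.
2. In 5.3, change the entry to *all recorded adverse events*, since other events would still not be collected.
3. Leave 3.7 unchanged.
4. Report the number of contrast reactions descriptively with an exact 95% confidence interval.

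The cost is an amendment of a few lines and, for the contrast reactions, about 0 to 6 more spreadsheet rows at the assumed rates, filled from observation already required. Requiring every related or possibly related event, serious or not, would cost more. Under 1.1 it would take in needle-site discomfort and anxiety, and an infection at the IV site would not normally appear within 30 minutes. The narrower rule avoids this, at the price of not capturing non-serious reactions that begin later.

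If the serious-only filter is kept, the minimum is change 2 and a sentence in 3.1 stating whether related includes possibly related.

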**3.2 How will adverse event data be collected/recorded?**

Spreadsheet: paper or electronic

**3.3. How will AEs be classified/graded?**

Mild/Moderate/Severe

Serious/Not serious **Required for all protocols**

**3.4 What scale will the PI use when evaluating the relatedness of adverse events to the study participation?**

The PI will determine the relationship of adverse events to the study using the following scale:

Related: AE is clearly related to the intervention

Possibly related: AE may be related to the intervention

Unrelated: AE is clearly not related to intervention

**3.5 When will recording/reporting of adverse events/unanticipated problems begin?**

After subject begins study intervention

**3.6 When will the recording/reporting of adverse events/unanticipated problems end?**

End of study participation

**3.7 How will Adverse Events, Unanticipated Problems, Protocol Violations and Data Breaches be reported? Complete the table below to answer this question**

Type of Event	To whom will it be reported:	Time Frame for Reporting	How reported?
Any internal event resulting in death that is deemed DEFINITELY related to (caused by) study participation An internal event is one that occurs in a subject enrolled in a UVa protocol	IRB-HSR	Within 24 hours	IRB Online and phone call www.irb.virginia.edu/
Internal, Serious, RELATED, Unexpected adverse event	IRB-HSR	Within 7 calendar days from the time the study team received knowledge of the event.  Timeline includes submission of signed hardcopy of AE form.	IRB Online www.irb.virginia.edu/
Unanticipated Problems that are not adverse events or protocol violations This would include a Data Breach.	IRB-HSR	Within 7 calendar days from the time the study team received knowledge of the event.	Unanticipated Problem report form.  http://www.virginia.edu/vprgs/irb/HSR_docs/Forms/Reporting_Requirements-Unanticipated_Problems.doc
Protocol Violations/Noncompliance The IRB-HSR only requires that MAJOR violation be reported, unless otherwise required by your sponsor, if applicable.  OR Enrollment Exceptions See definition- only allowed if	IRB-HSR	Within 7 calendar days from the time the study team received knowledge of the event.	Protocol Violation, Noncompliance and Enrollment Exception Reporting Form  http://www.virginia.edu/vprgs/irb/hsr_forms.html  Go to 3rd bullet from the bottom.

there is a commercial sponsor or a DSMB that has granted the enrollment exception.
			

Data Breach
	
The UVa Corporate Compliance and Privacy Office
 
ITC: if breach involves electronic data
 
Police if breach includes items that are stolen:
 
Stolen on UVA Grounds
 
OR
 
Stolen off UVa Grounds- contact police department of jurisdiction of last known location of PHI
	
As soon as possible and no later than 24 hours from the time the incident is identified.
 
As soon as possible and no later than 24 hours from the time the incident is identified.
 
IMMEDIATELY.
	
UVa Corporate Compliance and Privacy Office- [contact]
 
ITC: Information Security Incident Reporting procedure, http://www.itc.virginia.edu/security/reporting.html
 
UVa Police-Phone- [contact]

